While the evidence seems to support a relationship between a change in microbiota and NEC, there is no clear relationship between anemia or transfusion and NEC. There have been no studies evaluating the relationship between anemia or transfusion and a change in microbiota. That is the primary focus of this study.

Hypothesis:

Anemia will result in alteration of the stool microbiota. Transfusion will return microbiota to baseline. The specific alteration in microbiota with anemia may include: increase in *Proteobacteria*, decrease in *Firmicutes*, and/or decrease in microbiota diversity.

Primary Outcome:

- Change in microbiota with anemia

Secondary Outcome:

- Change in microbiota after transfusion

Inclusion Criteria:

- Preterm infants less than 32 weeks gestation at birth
- ≥ 7 days and <30 days on enrollment
- On minimum 100mL/kg enteral feeds

Exclusion Criteria:

- NEC prior to enrollment
- Prior surgery
- Major congenital anomalies
- Oxygen requirement with $\text{FiO}_2 > 50\%$

Methods:**Definitions:**

- Severe anemia will be defined as a hematocrit $< 25\%$.
- Anemia will be defined as a hematocrit ≥ 25 and $<30\%$.
- No anemia will be defined as a hematocrit $\geq 30\%$.

Hematocrit will be tested per patient's care team. In this unit, hematocrit is usually obtained every Monday, and sometimes more frequently.

Sample Collection:

- Collect stool samples weekly (Sunday, Monday, or Tuesday)
- Collect stool samples 1, 4, and 7 days post-transfusion
- Stool will continue to be collected until infants are 38 weeks corrected gestational age (CGA) or discharge (whichever is earlier).

Data Collection:

Hematocrit	Gestational Age
Birthweight	Apgars
Sex	Race
Singleton/Multiple	Age at stool collection and at hematocrit blood sampling
Iron supplementation	Type of feeds (breastmilk/formula feed)
Calorie fortification of feeds	Total days on antibiotics
Number of transfusions	Positive cultures
NEC	Indomethacin exposure

Groups:

Paired samples will be obtained from the same infants, one before and one after onset of anemia. Therefore, the patients will serve as their own controls.

Sample Analysis:

- Stool samples obtained while patient is on antibiotics will not be included in analysis since the microbiota is expected to be significantly changed with large populations wiped out. Stool samples obtained 5 days after completion of antibiotics will be included in analysis again since infants are expected to be recolonized by that time.

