- qRT-PCR of samples will be performed to quantify the major bacterial groups: *Proteobacteria*, *Firmicutes*, and *Bacteroides*.
- Next generation sequencing will be done for qualitative analysis and metagenomics profiling of bacteria

Informed Consent:

New admissions to the Parkland NICU will be screened for recruitment if their birth gestational age (OB assigned) is less than 32 weeks 0 days and if they are at least 7 days old.

- If they meet these two criteria, they will be screened to ensure they do not meet exclusion criteria.
- If they do not meet the exclusion criteria, then their feeds will be evaluated. If they are on at least 100mL/kg/day of enteral feeds, then they will be approached for recruitment. Infants that are not yet on 100mL/kg/day of enteral feeds will have their charts assessed daily until 29 days of life. If and when they achieve 100mL/kg/day of enteral feeds, they will be approached for recruitment. If an infant does not achieve 100mL/kg/day of enteral feeds before 30 days of life, they will not be approached for enrollment in this study.
- If an infant meets the above criteria, and once their parent/guardian/LAR provides consent, then stool collection will begin for that infant from the next available defecated diaper. In cases where the patients are not the PI's patients, the study team will inform all the physicians caring for the patients within the NICU about this research study and

once they approve for their patients' (infant's) parents/guardians/LARs to be approached for consenting purpose to enroll the infant into this study, the bedside nurse will check with the parents/guardians/LARs if they would like to be approached. Once they let the beside nurse know if they agree to be approached, the nurse would inform this to [name] (the PI) and [name] (study team) who will be responsible for recruitment of subjects and they would approach the patient's parent/guardian/LAR for consenting purposes.

Sample Size Calculation:

Group sample sizes of 194 achieve 80% power to detect an odds ratio of 1.500 in a design with 2 repeated measurements having a simple covariance structure when the proportion for group 2 is 0.4 and group 1 is 0.5. The alpha level is 0.05.

Statistical Analysis:

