Descriptive analysis will use percentages, means, medians, and measures of variability to describe demographic data. Categorical factors will be evaluated using Chi-square or Fisher exact test between the groups. Continuous factors will be evaluated using Student's t-test or Mann-Whitney U test if the data is non-normal distributed between the groups. Repeated measurements will use analysis of variance (ANOVA) to compare groups. The statistical significance level will be 0.05 for all statistical tests.

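### An unadjusted 0.05 for every test leaves chance findings uncontrolled if the sequencing taxa are compared one by one

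*Protocol*

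**What the plan says.** All references are to the protocol.

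- **Statistical Analysis:** "The statistical significance level will be 0.05 for all statistical tests". The methods named are chi-square or Fisher, t or Mann-Whitney, and ANOVA for repeated measurements. Each takes one variable at a time. The section has no multiplicity adjustment, no false discovery control, no exploratory label and no test of overall composition.
- **Sample Analysis:** two laboratory streams are planned. For the first, "qRT-PCR of samples will be performed to quantify the major bacterial groups"; three groups are listed. For the second, "Next generation sequencing will be done for qualitative analysis and metagenomics profiling of bacteria".
- **Primary and Secondary Outcome:** these are an alteration of the microbiota with anemia and after transfusion, with no taxon, index or composition measure named.
- **Hypothesis:** more Proteobacteria, fewer Firmicutes and a "decrease in microbiota diversity" are offered as possibilities, any one of which or any combination would count.
- **Sample Collection:** stools are taken weekly and on three days after each transfusion (1, 4 and 7).
- **Sample Size Calculation:** "Group sample sizes of 194 achieve 80% power to detect an odds ratio of 1.500", and "The alpha level is 0.05".

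**The concern.** A sequencing profile can yield many taxa. Three features of the protocol act together: a significance rule that covers every test, outcomes that any taxon could satisfy, and a list of one-variable methods with no overall test in front of them. Applied to a profile, those methods work feature by feature, and the stated rule then accepts each feature at 0.05 however many are examined.

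At stake is how far a list of altered taxa can be believed. The protocol says that no study has yet examined anemia or transfusion against the microbiota, so there would be no earlier results to check such a list against. Its Background also links dysbiosis to necrotizing enterocolitis, so a chance list could be given clinical meaning.

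The protocol states this rule; it has not left the matter open. A later analysis plan that added false discovery control would at least have to qualify the sentence as it stands.

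**Working it through.** **1. The plan's own figure.** The inputs are proportions 0.5 and 0.4, two uncorrelated measurements ("in a design with 2 repeated measurements having a simple covariance structure"), alpha 0.05 taken as two-sided, and power 80%. With the pooled-variance formula:

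n = [1.960 × √(2 × 0.45 × 0.55) + 0.842 × √(0.25 + 0.24)]² / 0.10² ≈ 387.3, rounded up to 388 observations per group.

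388 / 2 = 194, which matches the protocol. The odds ratio is (0.5/0.5)/(0.4/0.6) = 1.50, and power at 388 observations is 0.801. The calculation therefore spends the full 0.05 on **one** binary comparison. It makes no allowance for a profile of taxa.

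**2. Taxa compared individually.** Let m be the number of taxa tested in one contrast, all without a true change. Then:

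- expected false positives = 0.05 × m
- chance of at least one, if independent = 1 − 0.95^m
- chance of three or more, if independent = upper binomial tail with probability 0.05

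The protocol gives no m, so 10 to 200 is an assumed range.

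| m | Expected false | At least one | Three or more |
|---|---|---|---|
| 10 | 0.5 | 40.1% | 1.2% |
| 50 | 2.5 | 92.3% | 46.0% |
| 100 | 5.0 | 99.4% | 88.2% |
| 200 | 10.0 | over 99.9% | 99.8% |

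Correlation between taxa leaves the expected count unchanged but alters the two probability columns.

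**3. The measures the protocol names.** Three qRT-PCR groups plus diversity make 4 tests per comparison:

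- one comparison, 4 tests: 1 − 0.95⁴ = 18.5%; expected 0.2
- anemia and transfusion, 8 tests: 1 − 0.95⁸ = 33.7%; expected 0.4
- two anemia grades and three post-transfusion days each tested separately, 4 × 5 = 20 tests: 1 − 0.95²⁰ = 64.2%; expected 1.0

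The third count is an upper reading, since the protocol does not plan those separate tests. This short, named list produces at most about one chance finding. Larger counts arise only from the profile.

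**4. Effect of the fix.** Benjamini-Hochberg at 5% compares the k-th smallest of m p-values with 0.05 × k/m and declares every taxon up to the largest k that passes. With m = 100, a single declared taxon needs p ≤ 0.0005, and ten declared taxa need the tenth smallest p ≤ 0.005.

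**The case against.** The strongest objection is that the taxon-by-taxon screen is an inference. The protocol gives quantification to qRT-PCR of three groups, describes sequencing as qualitative analysis and profiling, and never mentions taxa in its statistical section. This stands, and it is why the point is conditional.

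Two stronger readings are tempting, and the document supports neither.

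- **A reader might infer that the sequencing part is bound to report several false taxa.** That needs a number of taxa the protocol does not give. The only count in the Background points low: four classes hold more than 90% of neonatal gut microbes. With 4 tests the expected number is 0.2, and with 10 it is 0.5. Three or more false taxa become likely only above roughly 50 null tests.
- **A reader might infer that days 1, 4 and 7 repeat the screen three times**, giving 4 × 100 × 0.05 = 20 false taxa over four contrasts of 100. Those are stool collection days. The ANOVA for repeated measurements could be one test across time, so this figure does not follow from the text.

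A further objection is that taxonomic level, filtering and false discovery control usually belong in an analysis plan, which is not shown here, and that a 0.05 level can be applied to adjusted p-values. This is right for the details, and their absence is not criticised. It does not remove the problem with the sentence itself, which covers all tests and mentions no adjustment.

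Finally, confining 0.05 to a single primary comparison would be a poor repair. The primary outcome names no single measure, and the qRT-PCR comparisons after transfusion would be left without a level. This also stands, and the fix below is framed accordingly.

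**Conclusion.** The concern holds in conditional form. The protocol fixes an unadjusted 0.05 for every test while planning a metagenomic profile under outcomes that name no measure. If taxa are compared individually, about 5 in every 100 null comparisons will be significant by chance: 0.5, 2.5, 5 and 10 expected per contrast for 10, 50, 100 and 200 taxa, and more if the post-transfusion days are tested separately.

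These figures assume that none of the tested taxa truly changes and that the number of taxa lies in the range shown. The expected counts do not need independence; the probabilities do. The protocol does not show that each taxon, or each post-transfusion day, will be tested on its own, so no particular number of false findings can be attributed to the plan. The sentence should be corrected. The problem touches neither sample collection nor the arithmetic behind the group size of 194.

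**What to change.** Replace the single sentence on the significance level with wording such as:

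*The 0.05 level applies to the prespecified comparisons of the qRT-PCR bacterial groups and of diversity, for anemia and for transfusion. Taxon-level results from sequencing are exploratory and are declared at a Benjamini-Hochberg false discovery rate of 5% across all taxa and contrasts tested.*

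Optionally, add one overall composition test per contrast, permuted within infant to respect the paired design, before any taxon is examined. Taxonomic level and any prevalence filter can be left to the analysis plan.

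The qRT-PCR and diversity comparisons would still carry the family-wise error shown above (33.7% for 8 tests), so they should be listed in advance and all reported. This fix separates them from the open profile but does not adjust them.

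The cost is two sentences of analysis wording, with no change to samples, assays or sample size. The downside is that fewer taxa will be declared significant, and weak true changes may be missed.
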